### THERAPEUTIC REGIMENS:

Patients will be randomized according to a 1:1 ratio to treatment arms A and B.

- Arm A: regorafenib until disease progression or unacceptable toxicity occurs, followed by trifluridine/tipiracil until disease progression or unacceptable toxicity occurs.
- Arm B: trifluridine/tipiracil until disease progression or unacceptable toxicity occurs, followed by regorafenib until disease progression or unacceptable toxicity occurs.

Prior to randomization, they will be stratified according to:

- Country
- ECOG (0 or 1)
- Age (<65 years old or  $\geq$ 65 years old)

The time span between the end of the first treatment phase and the initiation of second treatment phase should not exceed 4 weeks.

Protocol nº: UC-GIG-1910 - version nº3.0 – 10 February 2022

Page 6/12

The posology of regorafenib will be as follows: 80mg per day on C1W1, 120mg per day on C1W2, 160mg per day on C1W3, 1 week off (this 4-week period is considered a treatment cycle), followed by regorafenib 160 mg starting from cycle 2.

If a dose is missed, then it should be taken on the same day as soon as the patient remembers. The subject should not take two doses on the same day to make up for a missed dose. In case of vomiting after regorafenib administration, the subject should not take additional tablets.

The starting dose of trifluridine/tipiracil is 35 mg/  $m^2$ /dose administered orally twice daily on Days 1 to 5 and Days 8 to 12 of each 28-day cycle. The dosage is calculated according to body surface area. The dosage must not exceed 80 mg/dose

If doses are missed or held, the subject must not make up for missed doses.

Posology adjustments

## Regorafenib

The regorafenib dose may be delayed or reduced in case of clinically significant hematological and other toxicities that are considered at least possibly related to regorafenib. Toxicities will be graded using the NCI-CTCAE v5.0. Regorafenib dose will be modified in increments of 40 mg. The lowest recommended daily dose of regorafenib is 80 mg and the maximum is 160 mg. Thus, if a patient experiences more than two dose reductions, regorafenib should be permanently discontinued.

[figure not shown]
If a patient experiences several toxicities with conflicting recommendations, the recommendation with the lowest dose of regorafenib to be taken must be used. Recommendations are described in the protocol and in the SmPC. You should always refer to the most recent version of the SmPC for regorafenib (Stivarga®).

[figure not shown]
## Trifluridine/tipiracil

A maximum of 3 dose reductions are permitted to a minimum dose of  $20 \text{ mg/m}^2$  twice daily. Dose escalation is not permitted after it has been reduced.

In the event of haematological and/or non-haematological toxicities patients should follow the dose interruption, resumption and reduction criteria stated in the SmPC. You should always refer to the most recent version of the SmPC for trifluridine/tipiracil (Lonsurf®).

Treatment will be discontinued in case of any delay in treatment administration of more than 4 weeks. **TRIAL FLOWCHART:** 

**DOSE ESCALATION :** No dose escalation possible

## E) STATISTICAL ANALYSIS PLAN

#### **REQUIRED NUMBER OF PATIENTS TO BE SCREENED/INCLUDED:**

The primary endpoint is the feasibility of the treatment sequence. The hypothesis for the sample size calculation are based on the data published by Moriwaki et.al showing that 50% of the subjects receiving trifluridine/tipiracil were able to receive further treatment as compared to 65% with regorafenib (Moriwaki, Fukuoka et al. 2018). With a Chi-square test between the two arms, a bilateral type I error rate of 5% and a power of 80%, 170 patients are required in each arm, i.e. 340 patients in total.

E

#### STATISTICAL ANALYSIS:

#### **Study population**

The following populations will be considered:

- Intent-to-Treat (ITT) population will include all randomized patients according to their randomized arm. This population will be used for the analysis of all efficacy endpoints.
- The safety population will include all the patients who have received at least one dose of either drug regardless of treatment period. This population will be used for the safety analysis.

#### Statistical analysis plan

Statistical data will be presented in the form of:

- percentages for qualitative variables,
- mean and standard deviation or median and range for quantitative variables.

The baseline characteristics of the trial arms will be described, including demographics and laboratory measurements, using descriptive statistics.

All tests will be bilateral tests with a 5% threshold.

All analyses will be performed by using SAS® version 9.4 or newer.

#### Primary endpoint analysis

The feasibility of the treatment sequence is defined as the percentage of patients who receive at least two cycles of both treatments in each arm, i.e. percentage of patients being treated until the first tumor evaluation. Thus, patients in Arm A, allocated regorafenib then trifluridine/tipiracil, will be considered a success if they received at least two cycles of regorafenib and two cycles of trifluridine/tipiracil. Similarly, patients in Arm B, allocated trifluridine/tipiracil then regorafenib, will be considered a success if they receive at least two cycles of trifluridine/tipiracil and two cycles of regorafenib.

Whenever the patient did not receive the second treatment (i.e toxicity, death, lost to follow-up...), it will be considered as a failure.

The comparison between the two trial arms will be adjusted for the stratification factors with a logistic regression model according to the intent-to-treat principle.

## F) SAMPLES COLLECTED FOR TRANSLATIONAL RESEARCH – FRENCH SITES ONLY

#### SAMPLE TYPES:

#### TUMOR

- Collection of previously collected and archived paraffin-embedded **tumor samples** from patients in both arms at baseline visit, in order to identify tumor factors predictive of response using immunochemistry.

#### BLOOD

- Whole blood sample will allow the dosing of constitutional/genomic DNA (gDNA) at baseline visit.
- Plasma samples will allow the dosing of circulating tumor DNA (ctDNA) concentrations in order to
  predict tumoral response. Additional plasma samples will allow the dosing of Stanniocalcin-1 (STC1)
  in order to establish the correlation between clinico-molecular characteristics of patients and STC1
  levels.

Thus, for all patients in both arms: collection of **blood samples** (per patient) are summarized below:

- at baseline : 4 tubes: 1 for gDNA (whole blood), 2 for ctDNA (plasma) + 1 for STC1 (plasma)
- during the treatment phase at each study visit (before drug administration on Cycle X Day 1) : 2 plasma tubes (ctDNA) and at the visit corresponding to the first CT-scan evaluation (8 weeks after Phase 1 - Cycle 1 Day 1) : 1 tube of plasma (STC1)
- o at the change of treatment visit : 2 tubes of plasma (ctDNA)
- o at treatment discontinuation visit: 2 tubes of plasma (ctDNA)
- at progression : 1st progression occurring during treatment period 1 : 1 tube of plasma (STC1) and 2nd progression occurring during treatment period 2 : 1 tube of plasma (STC1)

### **G) TRIAL DURATIONS**

**INCLUSION PERIOD:** 2 years

**TRIAL TREATMENT PERIOD:** until disease progression or unacceptable toxicity (approximately 6 months of treatment for both lines of treatment)

**FOLLOW-UP:** 5 years after the last study treatment stops

**DURATION UNTIL PRIMARY ENDPOINT EVALUATION:** 3 years

**OVERALL TRIAL DURATION (INCLUDING FOLLOW-UP):** 7,5 years

# SCHEDULE OF VISITS AND ACTIVITIES (SOA)

VISITS	Baseline visit(s)	Visits during first treatment phase	Change of study treatment visit	Visits during the second treatment phase	Study treatment discontinuation visit	Long-term follow-up visits
Visit timelines	≤28 days before starting treatment	On D1 of each 28- day treatment cycle	≤4 weeks delay between first and second treatment phases	On D1 of each 28-day treatment cycle	30±7 days after second treatment discontinuation	Every 3±1 months for 3 years and every 6±1 months for 2 years
DRUG DISPENSING AND ACCOUNTABILITY		Х		Х		
Eligibility criteria	Х					
Signed informed consent form	X					
Randomization	Х					
PHYSICAL EXAMINATION	I				I	L
Assessment of all systems, vital signs (pulse and blood pressure), weight, and height a .	X 	Хр	X	Xp	X	Xc
ECOG PS	X 	X	X	X	X	Xc
Medical history	X					
Safety/toxicity (graded by CTCAE v5.0)	X	X	X	X	X	
Concomitant treatments	X	X	Х	Х	X	Xc
PARACLINICAL EXAMINATION	1					
Tumor assessment (CT scan by RECIST v1.1) d	X	X	X	X	X	
Electrocardiogram (12-lead)	X					
BIOLOGICAL TESTS						
Complete blood count with differential	X 	X	X 	X	X	
Blood electrolytes: sodium, potassium, chloride, calcium, and phosphate)	X 	Х	X 	X	Х	
Liver function tests: AST, ALT, bilirubin (total and direct), alkaline phosphatase, and GGT	X 	Xe	X 	Xe	Х	
Kidney function tests: creatinine (serum), and uric acid. Creatinine clearance estimated by Cockcroft-Gault equation.	X 	x	X 	X	X	
Proteinuria	X 	Х	X 	Х		
Pancreas function test: lipase, amylase	X 	Х	X 	Х	X	
Thyroid function tests: TSH, T3, and T4	X 	Х	X 	Х	X	
Coagulation panel: PT, INR, and PTT	X 	Х	X 	Х	Х	
Pregnancy test (urine or serum)	X 					

Protocol n°: UC-GIG-1910 - version n°3.0 – 10 February 2022

**G** 

VISITS	Baseline visit(s)	Visits during first treatment phase	Change of study treatment visit	Visits during the second treatment phase	Study treatment discontinuation visit	Long-term follow-up visits
Visit timelines	≤28 days before starting treatment	On D1 of each 28- day treatment cycle	≤4 weeks delay between first and second treatment phases	On D1 of each 28-day treatment cycle	30±7 days after second treatment discontinuation	Every 3±1 months for 3 years and every 6±1 months for 2 years
QUALITY OF LIFE						
QLQ-C30 f	X 	X	X	X	X	
BIOLOGICAL SAMPLES ANCILLARY STUDIES	(optional) – French	sites only				
Collection of previously collected tumor samples	X					
Plasma samples (ctDNA + STC1)	ctDNA (2 tubes) + STC1 (1 tube)	ctDNA (2 tubes) (+STC1 at 1 st CT- scan assessment – 1 tube)	ctDNA (2 tubes) (+ STC1 at progression – 1 tube)	ctDNA (2 tubes)	ctDNA (2 tubes) (+ STC1 at progression – 1 tube)	
Whole blood sample (gDNA)	gDNA (1 tube)					
a Height will only be collected at baseline; b During regorafenib treatment blood pressure mus c Only survival data, ECOG PS and subsequent tre d Tumor assessments will be performed at baseline e During regorafenib treatment liver function tests ( † Completed at baseline, every 8 weeks during treat  Must be performed within 14 days of starting the statistical  Must be performed within 7 days of starting the statistical  Must be performed within 7 days of starting the statistical  Must be performed within 7 days of starting the statistical  Must be performed within 7 days of starting the statistical  Must be performed within 7 days of starting the statistical  Must be performed within 7 days of starting the statistical  Must be performed within 7 days of starting the statistical  Must be performed within 7 days of starting the statistical  Must be performed within 7 days of starting the statistical  Must be performed within 7 days of starting the statistical  Must be performed within 7 days of starting the statistical  Must be performed within 7 days of starting the statistical  Must be performed within 7 days of starting the statistical  Must be performed within 7 days of starting the statistical  Must be performed within 7 days of starting the statistical  Must be performed within 7 days of starting the statistical  Must be performed within 7 days of starting the statistical for t	eatment if any will be e and then every 8 we AST, ALT, and bilirub tment, at the change study treatment.	collected during the long eeks (±7 days) until dise in [total and direct]) mus	g-term follow-up phase; ase progression; st be performed every 2 weeks	-	es;	

D: day; ECOG PS: Eastern Cooperative Oncology Group performance status; CTCAE: common terminology criteria for adverse events; CT: computed tomography; RECIST: response evaluation criteria in solid tumours; AST: aspartate aminotransferase; ALT: alanine aminotransferase; GGT: gamma-glutamyl transferase; TSH: thyroid-stimulating hormone; T3: free triiodothyronine; T4: free thyroxine; PT: prothrombin time; INR: international normalized ratio; PTT: partial thromboplastin time, QLQ-C30: quality of life questionnaire C30.

R3\_DOC\_45 - Version 5 du 07/11/2018

E-

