### C) TRIAL GENERAL INFORMATION

**INDICATION:** The study population will consist of male and female patients aged  $\geq 18$  years old with metastatic colorectal cancer after failure of fluoropyrimidine-, irinotecan-, and oxaliplatin-based chemotherapies, as well as EGFR and VEGF inhibitors in patients eligible for these treatments.

**TRIAL DESCRIPTION/DESIGN:** Multicenter, international, comparative, randomized, open-label, phase II study conducted in two parallel groups.

**PRIMARY OBJECTIVE:** The primary objective will be to compare the feasibility of the treatment sequences, regorafenib then trifluridine/tipiracil (Arm A) and trifluridine/tipiracil then regorafenib (Arm B). The feasibility will be assessed in terms of percentage of patients able to receive both line of treatment.

G-

Protocol n°: UC-GIG-1910 - version n°3.0 – 10 February 2022

**SECONDARY OBJECTIVES:** The secondary objectives include the comparison between arms of:

- The Overall Survival (OS).
- The Progression-Free Survival in the first treatment line (PFS1).
- The Progression-Free Survival in the second treatment line (PFS2).
- The Disease control rate (DCR).
- The Objective response rate (ORR).
- The Time-to-treatment failure in the first treatment line (TTF1).
- The Time-to-treatment failure in the second treatment line (TTF2)
- The quality of life using patient reported outcomes: QLQ-C30 version 3.0
- The time to deterioration of ECOG PS  $\geq 2$
- The tolerance of the treatment sequences (by computing the incidence of adverse events using CTCAE v5.0).

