#### SECONDARY ENDPOINTS:

- Overall Survival (OS) is defined as the time interval from randomization until death from any cause.
- Progression-free survival 1 (PFS1) is defined as the time interval from randomization until death or the disease progression observed in the first sequence of treatment in each arm, evaluated using RECIST v1.1.
- Progression-free survival 2 (PFS2) is defined as the time interval from randomization until death or the disease progression is observed in the later sequence of treatment in each arm, evaluated using RECIST v1.1.
- Disease control rate (DCR) is defined as percentage of patients with a best response that is not progressive disease (PD) (either complete response [CR], partial response [PR], or stable disease [SD]) during treatment. DCR will be assessed in each study arm
- Objective response rate (ORR) is defined as percentage of patients with a best response being either complete response [CR] or partial response [PR] during treatment. ORR will be assessed in each study arm.
- Time-to-treatment failure 1 (TTF1) is defined as the time from randomization to treatment discontinuation for any reason (including disease progression, treatment toxicity, patient preference, or death) during the first sequence of treatment in each arm.
- Time-to-treatment failure 2 (TTF2) is defined as the time from randomization to treatment discontinuation for any reason (including disease progression, treatment toxicity, patient preference, or death) during the second sequence of treatment in each arm.
- Quality of life data using the patient reported outcomes, QLQ-C30 version 3.0 will be collected during the study.
- The time to ECOG PS ≥2 deterioration is defined as the time interval between randomization and the first documented ECOG PS ≥2 during the study.
- Data concerning adverse events graded using the CTCAE v5.0 will be collected during the study.

These endpoints will be compared between the study arms.

D) INVESTIGATIONAL MEDICINAL PRODUCTS								
PRODUCT NAMES AND ADMINISTRATION:								
Drug name (INN)	Registered name 	Pharmaceutical form	Administration route		Posology			

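### In this open-label trial the baseline QLQ-C30 is timed only against treatment start, so the schedule permits it to be completed after the patient knows the arm

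*Protocol*

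**What the plan says.** The synopsis, section C, describes a "Multicenter, international, comparative, randomized, open-label, phase II study conducted in two parallel groups". Under Secondary endpoints, "Quality of life data using the patient reported outcomes, QLQ-C30 version 3.0 will be collected during the study", and the list closes with "These endpoints will be compared between the study arms".

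The timing of the questionnaire is set in the schedule of visits and activities:

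- The baseline column is headed "≤28 days before starting treatment". Randomization is ticked in it with no footnote and no stated order against the other baseline items.
- The baseline cell of the QLQ-C30 row carries superscript 2. That footnote begins "Must be performed within 7 days of starting the". The text is broken in extraction, but the anchor, start of study treatment, is legible.
- The QLQ-C30 row has its own footnote, which begins "Completed at baseline, every 8 weeks during treat" and goes on to the change of treatment. Its legible part does not mention randomization.

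Nothing legible sets a maximum interval between randomization and the first dose.

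**The concern.** In an open-label trial a patient-reported baseline is protected by randomization only if it is taken before the patient knows the allocation. After that, the score can reflect the patient's reaction to the arm as well as the state of health at entry. It is then a post-randomization measurement. Any difference between arms in it enters a change from baseline in full and a baseline-adjusted comparison in part. Analysis cannot recover the missing value, because a questionnaire completed late cannot be completed again at the right time.

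This is not a detail left to an analysis plan. Assessment timing belongs to the schedule, and the schedule does give a window here, counted from the wrong event. The same window has no reference date for a patient who is randomized but never dosed, although the intent-to-treat population includes all randomized patients.

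**Working it through.** The protocol gives no figure on this point to reproduce, and its sample size concerns the primary endpoint only. The check is of the timing rules, followed by the algebra of a late baseline.

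**1. What the window allows.** Count days backwards from the first dose. Let d be the day of randomization and q the day of the questionnaire. Footnote 2 gives 0 ≤ q ≤ 7. The questionnaire comes after randomization when q < d (on the same day, either order is possible).

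- If d > 7, every q inside the window is below d, so a compliant baseline necessarily follows randomization.
- If d ≤ 7, forms on days 7 down to d + 1 precede randomization and forms on days d − 1 down to 0 follow it. Both comply. At d = 7, any form on days 6 to 0 is post-randomization.

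**2. How large d can be.** The column heading alone would allow d up to 28, but other entries narrow this:

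- Inclusion criterion 9 requires blood count, liver, renal and coagulation results. The corresponding baseline tests carry superscript 2, the same 7-day window.
- ECOG is a stratification factor, so it must be known before randomization. Its baseline cell carries superscript 1 (14 days).

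Eligibility tests come before randomization. If l is the day of those tests, then d ≤ l ≤ 7 unless they are repeated before dosing. So d is usually at most 7, and the case d > 7 needs repeat tests.

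**3. What pulls the questionnaire before randomization.** Nothing legible does. Laboratory results and ECOG are needed to randomize; the QLQ-C30 is neither an eligibility criterion nor a stratification factor.

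**4. What a late baseline does.** Let s be the arm difference that knowledge of allocation produces in the baseline score, f the fraction of forms completed after disclosure, b the regression slope on baseline, and p the effect of the same knowledge on later scores.

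- Error in the change-from-baseline difference: p − f·s.
- Error in the baseline-adjusted difference: p − b·f·s.

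These errors are measured against an effect free of any reaction to allocation. Illustration, with s = 2 to 5 points on the 0–100 scale and b = 0.5 to 0.7, all assumed and none from the document:

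| Assumption | Change score | Adjusted |
|---|---|---|
| f = 1, p = 0 (reaction gone later) | −2 to −5 | −(0.5 × 2) = −1.0 to −(0.7 × 5) = −3.5 |
| f = 1, p = s (reaction persists) | 0 | (1 − 0.7) × 2 = +0.6 to (1 − 0.5) × 5 = +2.5 |

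With f below 1, the part due to the late baseline (f·s or b·f·s) shrinks in proportion. The sign of s is unknown as well. Neither size nor direction can be fixed.

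**The case against.** The strongest case against has four parts.

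- **Shared window.** The criterion 9 tests and the questionnaire have the same 7 days, so the natural reading is a single work-up before randomization. This stands in part. A reader might infer from the 28-day column heading that the schedule generally forces a post-randomization baseline. The document does not support that: 28 days is the outer limit for baseline visits, not a window for randomization, and the laboratory tests keep randomization near treatment start unless they are repeated. The order within those days is still left open, across 50 centers.
- **Incomplete text.** The footnotes are damaged by extraction, and the document is a protocol summary that refers to the protocol for detail. This stands as a limit. The fuller text may require completion before randomization; if so, the schedule should say the same.
- **Size.** A reader might also infer a bias of several points. That would need every form to be late and the reaction to allocation to disappear afterwards, on assumed shifts. Moreover, both arms are planned to receive both drugs and differ in order, so a differential reaction is less obvious than against placebo. This stands: no size should be claimed.
- **Unseen analysis.** The document specifies no change-from-baseline or adjusted QLQ-C30 analysis. True, but a baseline questionnaire is collected and the arms are to be compared. Any use of it as a reference inherits the problem.

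**Conclusion.** The point holds in a limited form. As legible, the schedule permits a baseline QLQ-C30 completed after the patient knows the arm, because its only time anchor is treatment start. It does not generally force one, and it does not show that this happens in practice. The size and direction of any resulting bias cannot be estimated from the document.

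The consequence is confined to quality of life, one of ten secondary objectives. The primary feasibility endpoint does not use the questionnaire. The conclusion rests on two assumptions: that the unreadable parts of the footnotes and the fuller protocol text contain no order rule, and that patients learn their arm at or soon after randomization, as is usual in an open-label trial. This is a cheap improvement to a secondary endpoint and does not threaten the trial's main result.

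**What to change.** In the QLQ-C30 row of the schedule, replace superscript 2 at baseline by a footnote requiring the questionnaire to be completed before randomization, before the arm is disclosed, and within the baseline period. Record the completion date, with the time if it falls on the day of randomization.

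For patients already enrolled, compare completion and randomization dates and report, by arm, how many baselines came after allocation.

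The cost is one footnote and a date check, with no extra visit or questionnaire. The downside is that in a few patients the baseline may precede treatment start by more than 7 days. The change also gives patients who are randomized but never dosed a defined baseline.
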